8.3 Subject Accountability and Disposition

The number of subjects randomized into the study (including summaries by treatment group and by stratum), in addition to the number of subjects included in each analysis set, will be summarized.

The number of subjects who have received study treatment in the ITT population, have ended the treatment, and the reason for ending treatment will be presented. The reason for discontinuing study will also be summarized.

8.4 Demographic and Baseline Characteristics

Summary statistics will be provided for demographics (age, sex, race, age group [<65 vs ≥ 65 and <75 vs ≥ 75], region and other baseline disease characteristics including FGFR3 mutation/fusion status, details on the mutation/fusion, lymph node involvement, stage at initial diagnosis, time from initial diagnosis to randomization, UTUC vs UBC and histology.

8.5 Medical History

A listing of medical history and current medical conditions will be provided, using the latest Medical Dictionary for Regulatory Activities (MedDRA) terminology available at the time of reporting. Medical history will also be summarized by system organ class (SOC) and preferred terms (PTs).

8.6 Prior Anti-cancer Therapy

Prior anticancer therapy will be summarized including prior neo-adjuvant chemotherapy (yes vs no), neo-adjuvant chemotherapy type, and other prior anticancer medication.

Prior cancer related surgery and its type will also be summarized, in addition to the time from the last prior cancer related surgery to randomization. Prior radiotherapy will be also summarized.

8.7 Protocol Deviations

The number (%) of subjects with any CSR-reportable protocol deviation will be tabulated by the deviation category for the ITT population.

8.8 Efficacy Analyses

The primary efficacy analysis will be conducted on the intent to treat (ITT) population, which will include all subjects who are randomized. Subjects will be analyzed according to the treatment group that they are randomized to.

All primary and secondary efficacy endpoints will be summarized as specified in General Principal Section 8.1. The analysis of time to event endpoints such as DFS, MFS and OS is specified in Section 8.1.

8.9 Sensitivity Analyses

Sensitivity analysis will not be performed for the abbreviated CSR.

8.10 Safety Analyses

Analysis of safety will be performed on the safety analysis population. Study data will be monitored on an ongoing basis by the clinical study team to ensure subjects' safety. Additional safety reviews will be performed by the data monitoring committee (DMC) periodically throughout the study. These reviews will include all available data on incidence of adverse events, serious adverse events including deaths. Study data will be monitored by QED's Global Safety Organization on an ongoing basis throughout the course of the study to identify potential safety signals and new events of interest. Any unblinding of serious adverse events (SAEs) by Global Safety due to regulatory requirements will be shared with the DMC.

8.10.1 Adverse Events

Treatment emergent AEs will be summarized. Treatment emergent AEs include all AEs that start on or after the first dose day of the study treatment and up to last dose day of the study treatment +30 days. All AEs collected in the AE electronic case report form (eCRF) page will be listed with treatment-emergent AEs flagged. In the body of this SAP treatment-emergent AEs are simply referred to as AEs, unless otherwise specified.

Adverse events will be summarized by number and percentage of subjects having at least one AE, having at least one AE in each primary SOC and for each PT using MedDRA coding. A subject with different National Cancer Institute (NCI) Common Terminology Criteria for Adverse Events (CTCAE) grades for the same preferred term will be summarized under the maximum CTCAE grade recorded for the event.

The following summary tables will be provided by treatment arm:

- Overall summary of AEs including the number and percentage of subjects with any AE, any serious AE, any AE leading to dose reductions/interruptions, any AE leading to discontinuation, and fatal AE.
- Summary of AEs by SOC, PT, and worst grade
- Summary of treatment-related AEs by SOC, PT, and worst grade.
- Summary of Grade 3 or 4 AEs by SOC, PT, and worst grade.
- Summary of serious AEs by SOC, PT, and worst grade
- Summary of serious treatment-related AEs by SOC, PT, and worst grade
- Summary of all AEs by PT in descending order of frequency
- Summary of treatment-related AEs by PT in descending order of frequency
- Summary of all Grade 3 or 4 AEs by PT in descending order of frequency
- Summary of SAEs by PT in descending order of frequency
- Summary of treatment-related SAEs by PT in descending order of frequency
- Summary of Common (10%) TEAEs by System Organ Class, Preferred Term and Worst Grade
- Summary of AEs leading to study treatment discontinuation by SOC, PT and worst grade
- Summary of AEs leading to study treatment discontinuation by PT in descending order of frequency
- Summary of AEs leading to dose reduction/interruption by SOC, PT, and worst grade
- Summary of AEs leading to dose reduction/interruption by PT in descending order of frequency
- Summary of fatal AEs by SOC, PT, and worst grade;
- Summary of fatal AEs by PT in descending order of frequency

- Summary of Common (10%) TEAEs by Preferred Term

The following listings will be produced:

- All adverse events
- All serious adverse events

The adverse events of special interest (AESI) will also be summarized. AESIs will include, but are not limited to calcium-phosphate homeostasis – hypercalcemia, hyper- and hypo-phosphataemia, ocular toxicity, cardiac toxicity, acute pancreatitis, pathological fracture, and tissue calcification.

Deaths

The primary reason for death will be summarized for on-treatment deaths (death occurs on or after first administration day of study treatment and within last administration day of study treatment +30 days), post-treatment deaths (death occurs after last administration day of study treatment +30 days), and all deaths for the safety analysis population.

All deaths will be listed for the safety analysis population, and on-treatment death will be flagged.

8.10.2 Concomitant Medications

Concomitant medications are defined as medications that subject have taken on or after the first administration day of study treatment and within the last administration day of study treatment +30 days. Concomitant medications will be coded using the World Health Organization (WHODrug) dictionary and summarized by Anatomical Therapeutic Chemical (ATC) classification and PTs.

8.10.3 Treatment Exposure

Duration of study treatment (last dose date – first dose date+1) and cumulative dose will be summarized by treatment arm. In addition, the relative dose intensity (cumulative actual dose/planned cumulative dose) will be summarized.

The number of subjects with prescribed dose holds or dose reductions and the reason for prescribed dose hold/reduction will be tabulated by treatment group. The summary of actual dose changes other than prescribed and the reason will also be summarized.

8.10.4 Laboratory Data Summary

Grade categorization of lab values will be assigned programmatically per CTCAE version 4 or later. A severity grade of 0 will be assigned for all non-missing lab values not graded as 1 or higher. Grade 5 is not applicable.

The laboratory summaries will include all lab assessments collected within the last administration day of study treatment +30 days. Laboratory parameters for hematology and blood chemistry will be summarized at baseline, selected post-baseline visit, the maximum and

minimum observed post-baseline values, and last observed value, along with the change from baseline. Lab shift tables will be done separately and labeled by direction.

In addition, number (%) of subjects with post-baseline laboratory abnormal results will be presented by grade for tests with CTCAE grading available and otherwise based on normal range. Incidence of potential drug-induced liver injury-based AST, ALT, TBL, AT, and bilirubin will be presented. Potential Hy's law cases will also be listed.

8.10.5 Ophthalmic Assessment

Both visual acuity score (logMAR) and tonometry will be summarized at baseline, each post-baseline visit (based on the visit schedule defined in the protocol along with a window), the maximum and minimum observed post-baseline values, and last observed value, along with the change from baseline.

Along with the summary described above, the number (percentage) of clinically significant changes in visual acuity score (logMAR) will be also summarized:

- <0.1 logMAR
- 0.1 - <0.2 logMAR
- 0.2 - <0.3 logMAR
- ≥ 0.3 logMAR

In addition, the number (percentage) of clinically significant values in tonometry will be summarized by visit:

- ≤ 21 mmHg
- > 21 mmHg

Number (%) of clinically significant abnormalities will also be summarized by visit for slit lamp, OCT and fundoscopy exams.

8.10.6 Left Ventricular Ejection Fraction (LVEF)

Left ventricular ejection fraction (LVEF) will be summarized for baseline, each post-baseline visit (based on the scheduled defined in the protocol along with a window), minimum post-baseline, along with the changes from baseline. Shift tables of the minimum post-baseline LVEF ($< 40\%$, 40% to 50% , $\geq 50\%$) with baseline LVEF status ($\geq 50\%$, $< 50\%$) will be provided.

Clinically significant changes of LVEF defined below will also be presented:

1. Absolute decrease from baseline $> 10\%$ but $< 20\%$ and LVEF $\geq 40\%$ to $< 50\%$
2. Absolute decrease from baseline $\geq 20\%$ and LVEF $\geq 20\%$ to $< 40\%$

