- h Ophthalmic assessment (performed by an ophthalmologist) will also be done as clinically indicated. Ophthalmic assessment includes visual acuity testing (including corrected distance acuity), slit lamp examination of the anterior eye segment, intraocular pressure, retinal OCT, and dilated fundoscopy. Additional examination methods such as specular microscopy and corneal pachymetry will be done as clinically indicated. Retinal OCT scans will be read locally and images will be provided to the OCT imaging vendor. Refer to the Study Manual for details regarding image collection and transfer or shipment. Ophthalmic assessment will be conducted at C13D28 or EOT visit unless performed within previous 4 weeks.
- i Full physical examination at screening, C1D1, and C13D28/EOT; abbreviated or symptom-directed physical examination at C2D1, C4D1, C7D1, C10D1, C13D1, every 6 months after EOT, and at the EOS visit.
- j For each subject, 12-lead ECGs will be done at Screening; predose on Day 1 of Cycles 1 and 2; and at C13D28 or EOT visit.
- k QOL assessments should be conducted before study drug administration, AE evaluation, and disease status notification, and preferably in order of EQ-5D-5L then EORTC QLQ-C30. Subjects should complete QOL assessments for 18 months; for subjects who complete all 52 weeks of study drug treatment, the last assessment will be at the first 6-month follow-up visit after discontinuation of study drug. Assessments do not need to be administered at the EOT visit if they were completed within the previous 7 days at a regularly scheduled visit.
- l Laboratory tests will be collected and analyzed on the scheduled day, even if study drug treatment is being withheld. Laboratory tests must be conducted within the windows specified in the protocol.
- m Hematology will be assessed at C1D1, C2D21, C4D21, C7D21, C10D21, C13D21, and C13D28 or EOT (refer to [Table 3](#)). Clinical chemistry will be assessed at C1D1, C1D4, C1D7, C1D14, C1D21; Cycles 2-13 (Day 21); and C13D28 or EOT (refer to [Table 3](#)).

The schedules for these clinical laboratory tests coincide, as closely as possible, with the blood draws specified for PK and cfDNA (refer to [Table 3](#)). Every attempt should be made to collect the clinical chemistry sample at the same time as the PK sample taken at 4 hours after study drug administration.

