 - a. Absolute neutrophil count (ANC) $< 1,000/\text{mm}^3$ ($1.0 \times 10^9/\text{L}$).
 - b. Platelets $< 75,000/\text{mm}^3$ ($< 75 \times 10^9/\text{L}$).

- c. Hemoglobin <8.5 g/dL; transfusion support is allowed if >1 week before randomization and hemoglobin remains stable.
- 13. Have insufficient hepatic and renal function:
 - a. Total bilirubin $>1.5 \times$ upper limit of normal (ULN) of the testing laboratory (for subjects with documented Gilbert syndrome, direct bilirubin must be $\leq 1.5 \times$ ULN and enrollment requires approval by the medical monitor).
 - b. AST/SGOT and ALT/SGPT $>2.5 \times$ ULN of the testing laboratory.
 - c. Serum creatinine $>1.5 \times$ ULN or a calculated (using the Cockcroft-Gault [C-G] formula [[Cockcroft 1976](#)]) or measured creatinine clearance of <30 mL/min.
- 14. Have amylase or lipase $>2.0 \times$ ULN.
- 15. Have abnormal calcium or phosphorus:
 - a. Inorganic phosphorus higher than $1.02 \times$ ULN of the testing laboratory.
 - b. Total serum calcium (can be corrected) higher than $1.02 \times$ ULN of the testing laboratory.
- 16. Have clinically significant cardiac disease including any of the following:
 - a. New York Heart Association (NYHA) Class $\geq 2B$; subjects with known history or current symptoms of cardiac disease, or history of treatment with cardiotoxic agents, should have a clinical risk assessment of cardiac function using the NYHA classification.
 - b. Uncontrolled hypertension (refer to European Society of Cardiology and European Society of Hypertension guidelines [[Williams 2018](#)]).
 - c. Presence of CTCAE v5.0 Grade ≥ 2 ventricular arrhythmias, atrial fibrillation, bradycardia, or conduction abnormality.
 - d. Unstable angina pectoris or acute myocardial infarction ≤ 3 months before the first dose of study drug.
 - e. Average QTcF >470 msec (males and females). Note: If the QTcF is >470 msec in the first ECG, a total of 3 ECGs separated by ≥ 5 minutes should be performed. If the average of these 3 consecutive results for QTcF is ≤ 470 msec, the subject meets eligibility in this regard.
 - f. History of congenital long QT syndrome.
- 17. Have had a recent (≤ 3 months before the first dose of study drug) transient ischemic attack or stroke.

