10.5 Safety Assessments

The safety evaluation will be based on AE reporting, laboratory parameters, vital signs, physical examinations, 12-lead ECGs, and ophthalmic assessments. Tolerability will be assessed by the incidence of AEs leading to study drug interruption, dose reduction, or discontinuation.

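### SAP 8.10.6 summarises LVEF on a visit schedule that the current protocol does not contain, and its categories of clinically significant change skip some larger falls while counting smaller ones (minor)

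*SAP*

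**What the plan says.** SAP 8.10.6 plans four things for LVEF.

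- A by-visit summary with change from baseline: LVEF "will be summarized for baseline, each post-baseline visit (based on the scheduled defined in the protocol along with a window").
- A summary of the minimum post-baseline value.
- A shift table of that minimum (below 40%, 40% to 50%, 50% or more) against baseline status (50% or more, below 50%).
- A count of notable changes: "Clinically significant changes of LVEF defined below will also be presented". Category 1 is an absolute fall of more than 10 but less than 20 points with LVEF from 40% to below 50%. Category 2 is a fall of at least 20 points with LVEF from 20% to below 40%. Category 3 is LVEF below 20%.

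SAP Section 1 ties the analysis to the protocol dated 19 May 2021. Section 10.5 of that protocol sets out the basis of safety assessment: "The safety evaluation will be based on AE reporting, laboratory parameters, vital signs, physical examinations, 12-lead ECGs, and ophthalmic assessments". The cardiac test in its schedule is the ECG: "12-lead ECGs will be done at Screening; predose on Day 1 of Cycles 1 and 2; and at C13D28 or EOT visit". For eligibility, subjects with a cardiac history, symptoms or cardiotoxic treatment "should have a clinical risk assessment of cardiac function using the NYHA classification".

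**The concern.** Two separate defects sit in one section.

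First, the SAP takes its LVEF visits and window from the protocol, and the current protocol supplies neither. A programmer has no visits to tabulate. A reader of the CSR could take a by-visit LVEF table, even a sparse one, as a sign that the protocol required LVEF monitoring. That matters a little more because SAP 8.10.1 names cardiac toxicity among the adverse events of special interest.

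Second, categories 1 and 2 each join one band for the size of fall to one band for the level reached. Combinations off that diagonal belong nowhere. A count labelled clinically significant can therefore include a subject and leave out another with a larger fall to a lower value.

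**Working it through.** The plan gives no figure to reproduce. The check is a search of the protocol followed by an enumeration of the SAP's own rules.

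**Step 1: is there an LVEF schedule in the protocol of 19 May 2021?**

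| Place in protocol | LVEF, echocardiogram or other ejection-fraction test |
|---|---|
| Tables 2 and 3 (schedules of assessments) | none |
| 9.3 screening | none |
| 9.5 treatment visits; 9.6 end of treatment | none |
| 9.7 and 9.8 follow-up | none |
| 10.5 safety assessments | none |
| 11.3.8.3 other safety findings | none |
| 6.2 cardiac exclusion criteria | NYHA class, blood pressure, rhythm and ECG criteria; no LVEF |

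LVEF is in the SAP's abbreviation list but not in the protocol's. By contrast, SAP 8.10.5 (ophthalmic) and 8.10.8 (ECOG) also refer to the protocol's visit schedule, and Table 2 does schedule those assessments. The general baseline rule in SAP Section 6 (last value before first dose) could be applied to LVEF, but the protocol requires no pre-dose measurement to apply it to.

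**Step 2: do the categories cover all falls?** Let b be baseline LVEF, m a post-baseline value and d = b − m, in percentage points.

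- Category 1: 10 < d < 20 and 40 ≤ m < 50
- Category 2: d ≥ 20 and 20 ≤ m < 40
- Category 3: m < 20

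| b to m | d | Category |
|---|---|---|
| 61 to 49 | 12 | 1 |
| 60 to 45 | 15 | 1 |
| 60 to 40 | 20 | none |
| 68 to 45 | 23 | none |
| 55 to 38 | 17 | none |
| 75 to 52 | 23 | none |
| 60 to 39 | 21 | 2 |

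Holding the baseline at 61 shows that the rule is not monotone. Values 49 down to 42 (d = 12 to 19) are category 1. Values 41 and 40 (d = 20 and 21) are in no category. Values 39 down to 20 (d = 22 to 41) are category 2. A subject who gets worse leaves the count and then re-enters it.

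The gaps are:

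- (a) d ≥ 20 with m still 40 or above;
- (b) 10 < d < 20 with 20 ≤ m < 40;
- (c) d > 10 with m still 50 or above, which overlaps (a) when d ≥ 20. The authors may have meant to exclude falls that end at 50 or above, but the SAP does not say so.

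**Step 3: extent of gaps (a) and (b) below 50%.** Take whole numbers with b = 50 to 75, m = 20 to 49 and d > 10.

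- Pairs: b = 50 to 60 gives 20 + 21 + … + 30 = 275; b = 61 to 75 gives 15 × 30 = 450. Total 725.
- Gap (a), m = 40 to 49: b = 60 to 69 gives 1 + 2 + … + 10 = 55; b = 70 to 75 gives 6 × 10 = 60. Total 115.
- Gap (b), m = 20 to 39: b = 50 to 58 gives 9 + 8 + … + 1 = 45.
- Uncategorised: 115 + 45 = 160, and 160/725 = 22%.

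If values of m below 20 are admitted, 26 × 20 = 520 pairs are added, all in category 3, and the share becomes 160/1245 = 13%. The share depends on the bounds chosen, so it describes the shape of the rule and not patients.

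**Step 4: the other two wording faults.** Category 3 contains no fall, so an unchanged 18% (b = 18, m = 18, d = 0) would be listed as a change. In the shift table a minimum of exactly 50% fits both 40% to 50% and 50% or more.

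**Step 5: what is still visible.** The 68 to 45 fall appears in the shift table as 50% or more to the middle band. The 55 to 38 fall appears as 50% or more to below 40%. Both also enter the minimum and change-from-baseline summaries.

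**The case against.** The strongest reply is that this is one descriptive section of a brief report on a study stopped for business reasons. SAP Section 5 tests no hypotheses, so no efficacy or error-rate conclusion depends on it. The table shells are in a separate document and may already deal with it. If there are no LVEF data, the category gaps have no effect. The 50% overlap is a slip, since the adjacent baseline split (50% or more, below 50%) shows what was meant. All of this stands and keeps the point minor. It does not repair a reference to a missing schedule or a rule that drops larger falls.

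A reader might also infer more than the documents support.

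- *That any LVEF values must be for-cause, or that LVEF was never collected systematically.* No section describes for-cause LVEF collection. The protocol's version history lists a version dated 3 September 2019, and first enrolment was estimated for December 2019, so some subjects may have entered under a version that is not available here. The SAP differs from the current protocol elsewhere (about 100 centres against about 165, and no mention of subjects who refuse cisplatin in its design section), so older text may have been carried over. Whether the 2019 version scheduled LVEF is unknown.
- *That 8.10.6 can simply be deleted at no cost.* If LVEF was collected under the 2019 version, deletion would drop safety data.
- *That cardiac safety rests on ECGs and cardiac adverse events alone.* Protocol Section 10.5 also includes vital signs and physical examinations.
- *That large falls are lost, or that 22% of patients are affected.* Step 5 shows where such falls still appear, and the 22% is a count of grid points.

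**Conclusion.** The point holds and is minor. The current protocol contains no scheduled LVEF measurement and no window, so the by-visit summary in SAP 8.10.6 has no basis in the protocol it cites. The categories miss falls of at least 20 points with LVEF still 40% or above, and falls of 11 to 19 points to an LVEF of 20% to below 40%, while smaller falls to higher values are counted. Category 3 and the 50% boundary are worded wrongly.

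The effect is confined to the count of clinically significant changes and to how the LVEF tables are read in the abbreviated CSR.

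The conclusion rests on the protocol of 19 May 2021 and the SAP as supplied. The eCRF, the table shells and the 2019 protocol were not available. The enumeration classifies one post-baseline value per subject; the SAP does not say whether a subject is classified on the worst value or on any value.

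**What to change.** 1. Reconcile SAP 8.10.6 with the protocol version(s) under which subjects were enrolled and with the eCRF, and state whether LVEF was a scheduled assessment.
2. If it was not, say so in the SAP and CSR, drop the by-visit and shift tables, and list any values collected with the number of subjects assessed per arm.
3. If LVEF is summarised, report per arm the number with a baseline and with at least one post-baseline value, and state which post-baseline value is classified. Redefine the categories so that every fall of more than 10 points is placed by the worse of its size and the level reached. With the SAP's own cut-points:
   - category 3: LVEF below 20% and lower than baseline;
   - category 2: otherwise, a fall of more than 10 points that is either at least 20 points or ends below 40%;
   - category 1: otherwise, a fall of more than 10 points.

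   All 160 uncategorised pairs in Step 3 then fall in category 2, and none of the 725 is left out. This also counts falls that end at 50% or above. If those are meant to be excluded, give them a separate labelled row.
4. Change the middle shift-table band to 40% to below 50%.

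The cost is a check of the eCRF and protocol versions, SAP wording, and an edit to the table shells. Every LVEF value that exists is still reported, in a table or a listing.
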